STUDY PROTOCOL

HPV PREVALENCE IN THE MOUTH AND OROPHARYNX OF THE TONSILLECTOMY POPULATION

ACRONYM: OROMOUTH

Version: 5.0 15-Jun-2015 Date: **Chief Investigator:** [name] Cancer Research UK Clinical Trials Unit (CRCTU) and Institute of Head and Neck Studies and Education **Study Coordinating Centre:** (InHANSE) Sponsor: University of Birmingham **Sponsor Reference Number:** RG12-208 **CRCTU Reference Number:** HN9001 West Midlands - Solihull REC Research Ethics Committee (REC): **REC Reference Number:** 11/WM/0283 **Ethics Approval Date:** 17-Oct-2011 **Funding Body:** Educational grant from GSK Biologicals

SIGNATURE PAGE

Oromouth Study Protocol version 5.0, 15-Jun-2015.

THIS PROTOCOL HAS BEEN APPROVED BY:

Name:	[name]	Role:	Chief Investigator
Signature:		Date:	DD/MON/YYYY

This protocol describes the Oromouth study and provides information about procedures for patients taking part in the Oromouth study.

AMENDMENTS

The following amendments and/or administrative changes have been made to this protocol since the implementation of the first approved version.

Amendment number	Date of amendment	Protocol version number	Type of amendment	Summary of amendment
1	03 rd Oct 2011	1.1	Substantial amendment	Ethical recommended amendment
N/A	04 th April 2012	1.2	Non-substantial amendment	Change in study contact details
N/A	26 th Jul 2012	1.3	Non-substantial amendment	Change in document formatting
2	06 th Sep 2012	2.0	Substantial amendment	Change of sponsor and rewording
3	10 th Dec 2012	3.0	Substantial amendment	Change in pilot study data use
4	20 th May 2014	4.0	Substantial amendment	Adapting to CRCTU template and clarification on study duration. Addition of SAE reporting section.
5	15 th Jun 2015	5.0	Substantial amendment	Change in recruitment target and extension of study.

STUDY SUMMARY

Title	HPV prevalence in the mouth and oropharynx of the tonsillectomy population
Design	Prospective cross-sectional study with a longitudinal sub-study
Aims	To determine the age and gender distribution of HPV detection in tonsils, oropharyngeal scrapes, nail brushings, oral fluid and urine and also the HPV antibodies in blood
Primary Objectives	 To estimate the overall, age and gender specific prevalence of HPV in the oropharynx in patients undergoing tonsillectomy for non-malignant conditions
Secondary Objectives	 To compare the HPV oropharynx prevalence between different sites—in order to identify the different reservoirs of HPV infection To describe the distribution of HPV seropositivity in the study population by age and gender To describe HPV-type distribution overall by age, gender, and sampling site To describe distribution by age and gender of patients who are both HPV PCR positive and anti-HPV L1 sero-positive – predicting persistent HPV infection To provide preliminary estimates of the clearance and persistence of HPV infection and antibodies in the oropharynx, as detected in follow-up oral fluid, finger tips/nail brushings and urine samples To assess the presence of anti-L1 HPV antibodies in saliva as a marker of vaccination or previous infection in the oral cavity To assess the presence of HPV in the urine To assess the presence of HPV in finger tips/nail brushings To provide preliminary evaluation of the performance of potential non-invasive tests for the detection of HPV infection in the mouth against HPV detection rates in tonsillectomy and oropharyngeal scrapes To identify the change in overall prevalence and distribution of HPV in tonsils over time, and to describe preliminary data on age and gender specific changes over time To provide preliminary data on the potential effect of HPV vaccination in the prevention of oral infection
Duration	6 months setup and pilot, recruitment over 36 months and 12 months for analysis
Population	Prospective cohort of up to 1000 eligible patients (minimum set of samples) undergoing tonsillectomy and a historical comparison group of 1250 patients who underwent tonsillectomy in early 2000's
Eligibility	 Inclusion criteria for prospective cohort: The following patients are eligible: Patients undergoing tonsillectomy for non-cancer reasons including operations for: recurrent tonsillitis, snoring surgery or obstructive sleep apnoea Age 0 to 65 years Patient or parent(s)/legal guardian(s) has given written informed consent/assent

	Exclusion criteria:
Eligibility	The following patients are not eligible to join the study: Patients undergoing adenoidectomy alone with no tonsillectomy Patients with previous oropharyngeal cancer or oral cancer, or any other head and neck cancer such as nasopharyngeal or laryngeal cancer that is currently undergoing or previously has been diagnosed or treated Learning disability preventing an adult over 16 years old from giving their own consent
Primary Outcome Measure	Occurrence of HPV in tonsil samples
Secondary Outcome Measure	 Occurrence of HPV in oral fluid, fingertip/nail brushings, oropharyngeal scrapes and urine samples Occurrence of HPV infection clearance in follow-up oral fluid, fingertip/nail brushings and urine samples collected at approximately 3 - 6 months after the first HPV positive sample Occurrence of persistent HPV infection in follow-up oral fluid, fingertip/nail brushings and urine samples collected at approximately 3 - 6 months after the first HPV positive sample Occurrence of HPV infection detected in follow-up oral fluid, fingertip/nail brushings and urine samples collected at approximately 3 - 6 months after the first HPV negative sample Occurrence of anti-HPV L1 antibodies in serum Occurrence of anti-HPV L1 antibodies in oral fluid sample
Study procedures and sample collection	 Study questionnaire – if 16 years old or over Oral fluid samples 20ml blood serum sample in adults >16years, 10ml blood in child <16 years old; 20- 30ml urine sample Finger tips/nail brushings Oropharyngeal scrape samples: posterior pharyngeal wall and base of tongue Tonsillectomy specimen Longitudinal subset: second oral fluid, finger tips/nail brushings and urine samples 3-6 months after operation

CONTACT NAMES AND NUMBERS

Key Contacts

Chief Investigator: [name]

College of Medical and Dental Sciences

School of Cancer Sciences University of Birmingham

[name]

[contact]

Email: [contact]

[contact]

Laboratories

DDL Diagnostic Laboratory:

Diagnostic Service Unit [name] The Netherlands [contact]

[contact] E-mail: [contact]

Study Statistician:

[name]

Center for Cancer Prevention

Wolfson Institute of Preventive Medicine Queen Mary University of London

[name]

[name]

[contact] E-mail: [contact]

Universiteit van Antwerpen:

Vaxinfectio – CEV

[name]

[name] Belgium

[contact]

Study Manager/Coordinator:

[name]

College of Medical and Dental Sciences

School of Cancer Sciences
University of Birmingham
[name]

[contact]

E-mail: [contact]

[contact]

GlaxoSmithKline Vaccines:

Clinical Immunology

R & D Department/Building 7

[name]

[name] - Belgium

[contact] [contact]

E-mail:

[contact]

Sponsor:

Research Governance and Ethics Manager

University of Birmingham

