7. STUDY PROCEDURES AND SAMPLE COLLECTION

All samples should be collected in accordance to the study procedure manual developed by GSK with details of sample collection kits, volume of samples to be collected and storage temperature requirements.

For a patient to be eligible for inclusion in the data analysis, the following samples are a minimum requirement:

- Oral samples
- Blood
- Oropharyngeal brushings
- Tonsils

 After written consent is obtained, the patients (above 16 years old only) will complete a short study questionnaire including age, gender, history of tobacco/alcohol use, sexual history including age of start of sexual intercourse, lifetime numbers of sexual partners, engagement in oral sex and lifetime number of oral sex partners etc.

- 2. An HPV vaccination history will also be taken. Consent/assent will also be taken from the patient, parent(s) or their guardian(s), if applicable, to obtain the patient's HPV vaccination status from vaccine and medical health records from their GP and/or other relevant health and educational authorities. The data requested will include confirmation of HPV vaccination status, including dates, number of doses and the type of vaccine given.
- 3. Oral fluid samples will be collected for HPV PCR and HPV antibody tests, using an oral rinse and an exudate collection device respectively.
- 4. A 20 30 ml urine sample will be collected for HPV PCR test.
- 5. Blood serum will be taken for HPV and biomarker serology tests. This can be taken after the patient has been anaesthetised if necessary. 20 mls of blood will be taken from patients aged 16 years and above, 10 mls from patients below 16 years old.
- 6. Once the patient is anaesthetised, two brush cytology scrapings using cytobrushes (provided) will be taken: one from the posterior pharynx including above and below the soft palate so that the adenoidal area is included, and a second separate brush scrape will be taken from the back of the tongue (base of tongue).
- 7. Tonsillectomy will then be performed and the tonsillar tissue will be placed in 10% buffered formalin and sent to the pathology department for paraffin embedding according to a specific protocol.
- 8. Stratified sampling will be employed to ensure that sufficient numbers of patients are recruited from all age groups, especially the age groups between 10 and 20 years old.

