12.2. ANALYSIS OF OUTCOME MEASURE

The statistical analyses will be described in detail in a statistical analysis plan (SAP). All of the tests will be two-sided with an alpha level of 0.05.

12.2.1. PRIMARY OUTCOME:

The overall prevalence will be estimated as the number of patients with HPV detected in tonsils divided by the total number of patients with available samples. An exact 95% confidence interval will be computed. The prevalence per age and gender group will be calculated similarly.

The relationship between prevalence and age will be explored using logistic regression with the age as a continuous covariate and gender and centre as categorical covariate. The number of degrees (one, two, three) of the model and possible variable transformation (e.g. log-transformation of age) could be determine based on graphical analysis of prevalence versus age relationship and on model fit criteria (e.g. AIC).

12.2.2. SECONDARY OUTCOME:

The overall prevalence will be estimated as the number of patients with HPV detected in oral fluid, oropharyngeal scrapes and urine samples divided by the total number of patients with available samples. An exact 95% confidence interval will be computed.

The prevalence per age and gender group will be calculated similarly. Prevalence rate will be compared among centres using a Cochran-Mantel-Haenszel test with stratification by age group.

Relationship between the prevalence of HPV in tonsils and the prevalence of HPV in oropharyngeal scrapes, oral fluid, and urine samples will be analysed by computing kappa coefficient. Specificity, sensitivity, positive predictive value and negative predictive value of HPV detection in the different sample types will be derived using the oral sample results as the reference.

Relationship between presence of anti-HPV L1 antibody in oral fluid samples and occurrence of HPV in tonsils and/or in oropharyngeal scrape samples will be analysed by computing kappa coefficiency. Specificity, sensitivity, positive predictive value and negative predictive value of anti-HPV L1 antibody assay will be derived using the oral sample results as the reference.

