12.3. SAMPLE SIZE CONSIDERATIONS

An analysis of current literature suggests that in a population recruited between 1990 and 2000, the prevalence of oral HPV was about 6.5%, varying from 0% - 10%. However, in an analysis of oropharyngeal scrapes and oral washings, the prevalence of HPV detection was much higher at 31%.

Pilot data of patients having tonsillectomy at University Hospital Coventry over two 3-month time periods are shown below in table 3. The number of tonsillectomy operations performed at the Heart of England NHS Foundation Trust - is approximately 50% of that for University Hospital Coventry quoted below.

Table 5: The number of tonsillectomy operations performed at University Hospital Coventry.

Age Group*	Number of Monthly recruitment (%)		
0-4	7 (12%)		
5-9	12 (20%)		
10-14	7 (12%)		
15-19	10 (17%)		
20-24	6 (10%)		
25-29	5 (8%		
30-34	4 (7%)		
35-39	5 (8%)		
40-44	1 (2%)		
45-49	1 (2%)		
50-69	1 (2%)		
Total	59		

^{*}There was an equal distribution of males and females in the group.

We plan to enrol 925 patients. The precision of the overall prevalence estimate that would be achieved with such a number is summarised in Figure 1 for prevalence ranging from 1 to 31 %. For example, if the observed prevalence is 10 %, the 95 % confidence interval for the overall population will be 8.4 to 11.8 % corresponding to a relative precision of 17 %.

[figure not shown]

Figure 1: Precision (95% confidence interval) of the prevalence estimate versus the prevalence observed in a random sample of 1250 patients.

We will also undertake a stratified sampling strategy to allow comparisons between those aged 14 and under (non-exposed, approximately one third of the cohort), and patients over 14 years of age (exposed) to allow the determination of the age of acquisition of infection and the optimal age of start of vaccination. The stratified sampling strategy will recruit patient subgroups as follows:

Table 6: The stratified sampling strategy for patient recruitment.

Age group	Sample size (%)		
0-4	150 (16.5%)		
5-9	150 (16.5%)		
10-14	150 (16.5%)		
15-19	150 (16.5%)		
20-24	150 (16.5%)		
25-34	100 (11%)		
35-44	60 (5.5%)		
45-65	15 (1.0%)		
Total	925		

[figure not shown]

Figure 2: Precision (95% confidence interval) of the prevalence estimate versus the prevalence observed in a random sample of 100, 150, and 250 patients.

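### The prospective sample size is given as up to 1000 patients with the minimum sample set and as 925 enrolled; the two are not reconciled, and precision is tied to enrolment with no allowance for incomplete sets

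*Protocol*

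**What the plan says.** - **Study Summary, Population:** "Prospective cohort of up to 1000 eligible patients (minimum set of samples"). The figure is a ceiling and is labelled by sample completeness.
- **Section 12.3:** "We plan to enrol 925 patients". Table 6 is introduced with "The stratified sampling strategy will recruit patient subgroups as follows", and its bands sum to 925. Both statements count recruitment.
- **Section 12.3, precision:** "The precision of the overall prevalence estimate that would be achieved with such a number is summarised in Figure 1". The number meant is the 925 to be enrolled. The worked example is "if the observed prevalence is 10 %, the 95 % confidence interval for the overall population will be 8.4 to 11.8" %, with a relative precision of 17%. The Figure 1 caption refers to "the prevalence observed in a random sample of 1250 patients".
- **Section 7:** "For a patient to be eligible for inclusion in the data analysis, the following samples are a minimum requirement". The list is oral samples, blood, oropharyngeal brushings and tonsils.
- **Section 12.2.1:** the primary prevalence is "the number of patients with HPV detected in tonsils divided by the total number of patients with available samples".
- **Section 12.4 and Table 7:** about 80% power for the historical comparison, with 150 vaccinated women excluded and 1100 per cohort. The Study Summary and section 7.2 give the archive cohort as 1250 (approximately 1250 in section 7.2).

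**The concern.** Under the protocol's own rule in section 7, enrolled and analysed are different populations. Section 6 registers a patient once eligibility and consent are confirmed, and section 7 collects the samples after consent. A patient therefore counts as enrolled before it is known whether the set is complete. Recruitment starts at age 0, and blood is one of the required samples.

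The summary counts patients with the set and section 12.3 counts patients enrolled. A reader cannot tell which count defines the target, or whether 925 is meant to be the analysable number. Section 12.3 then treats the enrolled number as the one that delivers the precision, which holds only if no enrolled patient is lost from the analysis.

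Three things rest on the answer: the precision of the overall and age-specific prevalence (the primary objective), the power of the historical comparison, and the timing of the interim analysis. Section 12.5 sets the interim at about half of target recruitment, which is 462.5 (about 462) on a target of 925 and 500 on a target of 1000.

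**Working it through.** **1. The target.** Table 6: 5 × 150 + 100 + 60 + 15 = 925. The section 12.3 total is reproduced. The gap to the summary is 1000 − 925 = 75. The two figures would match as enrolled and analysable only with a loss of 75/1000 = 7.5%. No such loss is stated, and the labels run the other way: 1000 carries the sample-set label and 925 the enrolment label.

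**2. The plan's own precision figure.** Section 12.2.1 specifies an exact interval, so I used Clopper-Pearson: lower limit = 2.5% quantile of Beta(x, n − x + 1), upper limit = 97.5% quantile of Beta(x + 1, n − x), with x = 0.10n (not rounded to a whole patient). Relative precision = half-width / 0.10.

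| n | Exact 95% CI at 10% | Relative precision |
|---|---|---|
| 1250 | 8.39 to 11.80% | 17.0% |
| 1000 | 8.21 to 12.03% | 19.1% |
| 925 | 8.14 to 12.12% | 19.9% |

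The stated 8.4 to 11.8% and 17% are reproduced at n = 1250, the number in the Figure 1 caption, and not at 925 or 1000. That is a separate inconsistency. Correcting it would still leave the target stated two ways.

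**3. Allowance for incomplete sets.** Analysable number = 925 × c, where c is the share of enrolled patients with the minimum set. The protocol gives no value for c; 95% to 80% is my assumption.

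| c | Analysable n | Exact 95% CI at 10% |
|---|---|---|
| 100% | 925 | 8.1 to 12.1% |
| 95% | 925 × 0.95 = 879 | 8.1 to 12.2% |
| 80% | 925 × 0.80 = 740 | 7.9 to 12.4% |

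**4. Historical comparison.** Formula: power = Φ[(d − 1.96·SE0)/SE1], two-sided alpha 0.05, unstratified and without continuity correction. Here d is the difference in prevalence, SE0 is the standard error under the pooled prevalence and SE1 the standard error under the two separate prevalences. The scenarios are the Table 7 rows: 2.0 v 4.1%, 5.0 v 8.1% and 8.0 v 11.6%.

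Table 7 first: 1100 v 1100 gives 82/84/81%, consistent with its stated 80%. With 925 enrolled and 150 vaccinated women removed, 925 − 150 = 775. First row against 1250 archive samples: pooled prevalence 0.0280, SE0 = 0.00755, SE1 = 0.00815, so power = Φ[(0.021 − 0.01479)/0.00815] = 78%.

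| Oromouth n after exclusion | v 1250 archive | v 1100 archive |
|---|---|---|
| 775 (all sets complete) | 78/79/76% | 75/77/74% |
| 879 − 150 = 729 (95% complete) | 76/78/75% | 74/76/73% |
| 740 − 150 = 590 (80% complete) | 72/73/69% | 70/71/67% |

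The last row removes all 150 from the complete patients. If the vaccinated women are incomplete at the same rate, 0.80 × 150 = 120 are removed, 620 remain, and power is 73/74/71% against 1250.

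**The case against.** Several points on the other side stand.

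- **A ceiling is not breached by a lower plan.** The summary says up to 1000, and 925 lies under it. The two numbers do not contradict each other arithmetically; the fault is that nothing relates them. For the same reason it would be wrong to say that 75 patients fall outside the age bands, since that treats a maximum as a target.
- **A reader might infer that 925 enrolled cannot yield 925 analysed.** The protocol does not support this. It never states that 925 will be analysed; it implies it by attaching precision to that number. If every set is complete, 925 enrolled gives 925 analysed. What can be said is conditional: any patient excluded for an incomplete set takes the analysis below 925.
- **A reader might infer that sites will close age bands at different points.** No section gives a band-closing rule or assigns band numbers to sites, and registration is confirmed centrally by the Study Office.
- **The primary denominator may be wider than section 7 suggests.** Section 12.2.1 divides by patients with available samples. If that means a tonsil sample, a missing blood or oral sample would not reduce the primary number. This could remove most of the loss for the primary outcome, but it is not how section 7 reads, so the two sections need aligning.
- **The effect on precision is small.** At 95% completeness the interval barely moves. Much of the fall below 80% power comes from Table 7's use of 1100 Oromouth patients, which is a separate matter from incomplete sets.

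None of this explains how 1000 relates to 925, or supplies the missing allowance.

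**Conclusion.** The point holds as an unreconciled sample size. The summary and section 12.3 use different numbers in different counting units, and section 12.3 rests its precision on enrolment although section 7 makes the minimum set a condition of analysis.

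The consequence for overall precision is modest: relative precision is about 20% at 925, and even at 80% completeness the interval widens only to 7.9-12.4%. The historical comparison is more sensitive. Even with all sets complete, 775 patients give 76% to 79% power against 1250 archive samples, or 74% to 77% against 1100. At 95% completeness about one further point is lost. At 80% the further loss against 1250 is about 5 to 7 points, depending on how the vaccinated women are removed.

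These losses rest on an assumed completeness, on section 7 governing the analysis set, and on an unstratified approximation to the planned stratified test. It does not follow that 1000 is an existing cap on enrolment: the summary attaches that figure to patients with the sample set.

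**What to change.** 1. State one target in one unit, either enrolled or with the minimum sample set, in the Study Summary, section 12.3 and Table 6, and say how 1000 relates to 925. The interim trigger in 12.5 then refers to that target.
2. Align the analysis rule in section 7 with the denominator in 12.2.1: say whether the primary prevalence needs all four samples or only a tonsil result.
3. Give the assumed completeness and its basis, and restate precision (12.3) and power (12.4, Table 7) for the expected analysable number, after removal of the vaccinated women where that applies.

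The 1000 should not be presented as an enrolment cap already in the protocol. Under that cap, 925 complete patients could be reached only with completeness of at least 925/1000 = 92.5%; at 80%, 925/0.80 = 1157 would have to be enrolled.

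The cost is wording and a short recalculation. No increase in enrolment is needed; the restated figures will be somewhat less favourable than those now printed.

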1. BACKGROUND AND RATIONALE

1.1. RAPIDLY INCREASING PUBLIC HEALTH PROBLEM

In the EU, oropharyngeal squamous cell carcinoma (OPSCC) currently accounts for 93,342 new cases (ASR-w of 6.9) and 42,962 deaths a year (ASR-w of 3.1) (Globocan 2008). It is estimated that in Eastern Europe, the burden of OPSCC is higher, with incidence rates in males of 9.1 per 100,000 (WHO HPV centre).

Worryingly, the incidence of OPSCC has been increasing dramatically in the EU and USA over the past decade. For example, the incidence of oropharyngeal cancer in England has more than doubled in the last decade (National Cancer Intelligence Network, 2010); whilst in Sweden it is increasing at the rate of 2% per year in men.

1.2. CAUSE OF THE PROBLEM

The rising incidence in Europe and the USA has recently been attributed to a new distinct disease entity called Human Papillomavirus-related oropharyngeal squamous cell carcinoma (HPV-OPSCC), caused by the Human Papillomavirus (HPV), which also causes most cervical and anal cancers (Mehanna, 2010). HPV infection is sexually-transmitted, and in the mouth may be linked to oral sex. Other bodily fluids e.g. saliva may potentially also be routes of transmission, especially before the onset of sexual activity. A meta-analysis of the world literature performed by our group shows that the proportion of HPV-OPSCC has more than doubled in Europe and the USA over the past decade (rising from 35% to 73% in Europe for example). Incidence in Europe and the USA is expected to continue to rise significantly due to the lag time between HPV infection and disease presentation (~25 yrs.), prompting concerns by some experts of an epidemic of viral-induced malignancy (Sturgis 2010).

